## 5. Subject Enrollment

1. Prescreening: There will be no prescreening of providers. Prescreening of patients will occur either prior to the visit during a phone call or at the time of the visit before the encounter if the potential participant is unable to be reached by phone. Please see the prescreening script for details.
2. Informed consent: We will obtain informed consent from providers and patients participating in the audiorecorded component of the pilot study for all providers who agree and for all patients who pass the prescreening as indicated in the script. We will

provide sufficient information to the prospective subjects about the nature of the study and their rights. Conversations about the informed consent process will occur by phone, by MGB zoom/Microsoft teams, or another MGB-approved videoconferencing platform, or in person. We will use REDCap eConsent using a Partners approved video platform or, we will do this in person either with REDCap or a paper form, depending on participant preference. The study staff will be present (either virtually or in person) for the consent process and will obtain either written or electronic informed consent from the participant using Partners approved REDCap e-consent/paperless consent process, or paper form if in person and the patient or provider prefers. REDCap eConsent will be sent securely using "Send Secure" to participants. The text will be "Please follow the below link to find the consent form. Thank you for your participation."

The consent process will be described as follows:

- 1) The IRB approved designees will explain the study to the subjects verbally, providing all pertinent information (purpose, procedures, risks, benefits, alternatives to participation, etc.) while allowing ample time for the potential subject to ask questions.
- 2) Following the verbal explanation, the potential subject will be provided with a written informed consent form and will be afforded sufficient time to consider whether or not to participate in the research.
- 3) After allowing sufficient time for the subject to read the informed consent form and think about their participation, we will answer any additional questions before asking them to sign indicating their agreement to participate in the research.

Once providers agree to participate, they will be randomized to either the intervention or the control arm. They will be stratified by site (MGH vs. BWH/ FH) and gender and then randomized using a random number generator. Providers in both arms will be asked to complete Implicit Association Tests and after, to watch a brief set of freely available educational lessons. Patients will not be directly randomized; they will be in the group assigned to their provider as this is a cluster randomized controlled pilot trial.

**Statement about informed consent:** We have included significant detail in our informed consent however do not provide in-depth explanations about unconscious bias (beyond stating the term) or the ways in which it may manifest itself in an encounter. In addition, we do not provide exact details about the individuation intervention for providers because we do not want to influence the behavior of those randomized to the control arm, and for patients because we want it to feel like an organic part of their encounter. We believe that the intervention (a strategy to help providers get to know their patients a bit better) is no more than minimal risk and that the absence of this specific level of detail in the consent form does not reduce the integrity of the consent or mislead participants.

## 6. STUDY PROCEDURES

### 1. Providers

Providers will be recruited and those who consent will be stratified by gender and site and randomized to the intervention or control arm. All providers in both arms will be asked to complete demographic surveys (either paper or on REDCap (with link sent using "Send Secure with the text "Please follow the below link to respond to the survey questions. Thank you for your participation.") and four Implicit Association Tests (IATs). Two of the tests assess biases related to race and two parallel tests assess biases related to socioeconomic status. As this is an interactive tool, we have instead attached the exact terms and instructions that will be used as an attachment. For each of the IATs, providers will be presented with a screen that has either the "cooperative" or "not cooperative" or "good" or "bad" linked with either "Black" or "White" for the race IATs and linked with "rich" or "poor" for the SES IATs. Providers will be prompted to, for example, click left for a bad term or photograph of Black individual, and right for a good term or photograph of a White individual, and then this will be reversed. The same will occur for the SES terms. IATs are standardized, well-accepted tools for measuring implicit bias (<https://implicit.harvard.edu/implicit/takeatest.html>). Millisecond

software/Inquisit web will be used to administer the tests because it allows for assessment of reaction time for correct classification, which is essential to IATs. Random IDs will be created using RedCAP or Qualtrics that are different from the participant IDs and will be stored on Millisecond/Inquist without any identifiable information. All identifiable information will be stored within the MGB Firewall on RedCap. After providers take the IATs and complete the baseline demographics form (under attachments), both arms will be given the link to freely available brief unconscious bias training module

(<https://stanford.cloud-cme.com/course/courseoverview?P=8&EID=20775>). This module has been approved by the MA Medical Society and is eligible for CME, which can be applied towards the unconscious bias training CMEs required for MA medical license renewal as of June 1, 2022. Upon completion of the unconscious bias module, providers in the intervention arm will meet with study team members to discuss their “individuation” countermeasure intervention and to view the brief presentation with a study team member about individuation. Providers will be given a choice of several individuation-related questions: “How do you spend a typical weekend day?”, “How do you spend a typical weekday?”, “What is your priority related to your health?”, “What are your hobbies/things you enjoy to do in your free time?” and “Can you describe something about yourself that you think makes you unique/different from other people?” to better understand the unique characteristics of each patient. The goal is that this will overcome the physicians unconscious stereotyping and allow them to see each patient as an individual as opposed to as a member of a certain racial or socioeconomic group. Once the provider decides on his/her choice phrases from the above list, the research team will assist with the development of a smart phrase (also called “dot phrase”) to allow them to incorporate this into a note. Once a week, providers in the intervention arm will receive an email reminding them to incorporate this question and the documentation into their clinic notes (see attachment of “Provider Reminder Email Script.”). We do not anticipate that these questions will include any answers that will place the research subjects at risk, but rather will allow their provider to get to know them better. This documentation will both allow for providers to be reminded of these individual characteristics at a later visit, and also allow the study team to review the notes to determine uptake of the intervention.

≥1 month after providers take the IATs, we will begin the process of recording 8-10 provider-patient interactions within each providers’ practice. This will occur at BWH or MGH Rheumatology main campus and satellite clinic sites. Providers will also be immediately informed before a patient encounter that will be recorded and will have the opportunity to decline. We anticipate encounters to last between 20-40 minutes. The vast majority of rheumatology outpatient encounters include only the provider and patient but if any other person is in the room (e.g., an observing medical resident), they will be asked for their permission as well. To record, a digital voice recorder (this one, or an equivalent from the MGB approved Staples vendor: [https://www.staples.com/Gpx-Pr047b-Digital-Voice-Recorder/product\\_2699228](https://www.staples.com/Gpx-Pr047b-Digital-Voice-Recorder/product_2699228)) or an MGB-encrypted iPad will be used (placed in the room by a research team member with both patient and provider aware, and collected immediately following the encounter), and all data will be transferred to the project-specific MGB secure drive at the end of each day and then

deleted from the device. For the iPad, the recording will be saved directly onto MGB Dropbox (and the MGB Dropbox app will also be used for the recording). These files will be transcribed verbatim using an MGB-approved vendor and all identifiable information will be removed. After 6 months, which is our estimate for recruitment time, providers will be asked to repeat the IATs. After completion of the study, providers will receive a one-time \$50 gift card or e-check.

## 2. Patients

Patients who consent to participate will be asked to have one clinical encounter with their provider recorded (preferably the next appointment) and then to complete a set of baseline surveys following that encounter including demographics, social determinants of health, everyday discrimination experiences, satisfaction with care, patient trust in the medical profession, patient perception of care centeredness and medication adherence. Surveys can be completed either via REDCaps via a link sent securely to the patient, or on paper forms (and then will be entered into REDCap by our study team). We will also assess medication adherence again 3 months after the encounter using a survey or a brief phone call, and over the 6-month period using the proportion of days covered data now available in the EMR. Patients will receive a \$30 gift card or e-check once the surveys are completed. We will also collect data from the patients' charts. These data include: demographics, social determinants of health, comorbidities/diagnoses, quality metrics related to their rheumatic disease, lab results, preventive care use (including immunizations), healthcare utilization (including ED visits, hospitalizations, outpatient visits and appointment no shows), medication use (including use of contraception as a quality metric), and medication refill data (proportion of days covered, available in the EMR) over the 6 months following the date of the recorded encounter. We will review the note from the date of the encounter and determine whether the individuation statement was documented in the intervention group.

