#### 4. Return of results

For providers, all data will be deidentified and analyzed in aggregate. Unique de-identified codes will be used for the provider IATs that will be linked with the provider-patient recordings. The PI and Co-Is will be blinded and only see de-identified data which will be used for analyses. This is to reduce any risk to the providers reputation or employment. One experienced, trained research assistant will be able to link the data to identifiers should an unexpected situation arise and make this necessary however the PI and Co-Is will be blinded in order to ensure that the reputation of providers in their practices is preserved. Results in aggregate will be presented in an end-of-study Grand Rounds to both the BWH and MGH rheumatology divisions (there is a combined grand rounds). The title of this grand round will be “Presentation of Findings from Breaking Implicit Bias Habits Intervention Study.” We will submit this presentation to the IRB for approval prior to the Grand Rounds. If we do find examples of implicit bias and explicit discrimination, we will work with MGB equity leadership in this area, who are aware of this study and have been part of these discussions (including [name], [name] and [name]) to determine the best Division-wide training tools to use to address this need.

For patients, data will also be de-identified for analyses and de-identified codes will link survey responses with the provider-patient encounter. However, we will be able to link survey scores back to patients and after the completion of the 3-month adherence study, we will provide them with a score report indicating what their scores on each of the respective surveys mean. A sample score report will be submitted as an amendment once we have analyzed surveys and have determined the best way to present these data.

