#### 5. Outcomes.

The primary outcome is documented receipt of high-quality care at the time of the appointment or within 30 days of the appointment (see Table 1). The items below will be added together to form a score and the number of items completed out of the total will be the primary outcome measure compared across groups. We will measure these data for all patients with SLE, osteoarthritis, and inflammatory arthritis including RA seen by the provider during the 6-month study period as well as do a separate subgroup analysis focused on the patients who had their appointments audiorecorded. We will use electronic medical record data obtained from chart review, from RPDR and from the Enterprise Data Warehouse (EDW) to obtain these metrics.

Table 1. Quality metrics for diseases of interest		
Systemic lupus erythematosus (SLE)	Rheumatoid Arthritis (RA)	Osteoarthritis
Hydroxychloroquine (HCQ) initiation If lupus nephritis, immunosuppressive initiation, ACE-I or ARB, glucocorticoids Glucocorticoid prophylaxis (e.g. PPI, calcium/vitamin D, PJP if high dose) Contraception if on teratogenic medication Vaccinations Baseline HCQ eye exam and monitoring labs	DMARD initiation, or bDMARD initiation Folic acid if receiving methotrexate Glucocorticoid prophylaxis Contraception if on teratogenic medication Baseline X-rays, TB and hepatitis screening Labs within 1 month of methotrexate initiation Documentation of disease activity measure Vaccinations	Annual functional status assessment Baseline exams Annual pain assessment Recommendation for assistive devices

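### Scoring of the note-based items in the primary quality score is not protected from knowledge of the study arm

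*Combined protocol and SAP*

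**What the plan says.** Section 6.5 (Outcomes) defines the endpoint by what is recorded: "The primary outcome is documented receipt of high-quality care at the time of the appointment or within 30 days of the appointment". Completed items from the quality-metric Table 1 are summed. On sources it says: "We will use electronic medical record data obtained from chart review, from RPDR and from the Enterprise Data Warehouse (EDW) to obtain these metrics". It does not say which item comes from which source.

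Some Table 1 items depend on what the provider writes. The rheumatoid arthritis (RA) column lists "Documentation of disease activity measure". The osteoarthritis column lists "Recommendation for assistive devices" together with functional status and pain assessments.

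Section 6.1 (Providers) has the research team help each intervention provider build a smart phrase for the chosen individuation question. It adds: "Once a week, providers in the intervention arm will receive an email reminding them to incorporate this question and the documentation into their clinic notes". Control providers get neither.

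Section 6.2 (Patients) lists the chart data, quality metrics included, and in the same paragraph says the encounter note will be reviewed to "determine whether the individuation statement was documented in the intervention group". Section 6.3 (Chart reviews) similarly lists the quality metrics and then a search for the smart phrases in patients who were not specifically enrolled.

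The masking statement is in Section 6.4 (Return of results): "The PI and Co-Is will be blinded and only see de-identified data which will be used for analyses". The reason given is protection of providers' reputation and employment. Section 10 says only that designated staff at one hospital collect and process the data.

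**The concern.** The smart phrase marks the arm inside the record from which part of the primary score is read. An abstractor who meets it, or who is checking uptake in a chart already known to belong to the intervention group, knows the allocation while deciding whether a sentence counts as a pain assessment or a device recommendation. The protocol contains no masking of abstractors, no removal of the phrase before scoring, no order for scoring and uptake review, no item-level scoring rules and no duplicate abstraction.

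Providers cannot be masked in this trial, so masked scoring is one of the few safeguards available. Without it, a difference in the score could partly reflect how notes were read, and the trial could not separate that from better care. The protocol intends this pilot to inform a larger multisite intervention, so the ambiguity would carry forward.

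**Working it through.** **1. The plan's own figure.** Section 9 gives 84% power for 0.5 SD with 10 providers per arm, two-sided alpha 0.05, and either ICC 0.02 with 8 patients per provider or ICC 0.05 with 10. Effective n per arm = k·m / (1 + (m − 1)·ICC), and SE = √(2/n) in SD units.
- ICC 0.02, m = 8: n = 80/1.14 = 70.2; SE = 0.169; power = Φ(0.5/0.169 − 1.96) = 84%.
- ICC 0.05, m = 10: n = 100/1.45 = 69.0; SE = 0.170; power about 84%.

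Both reproduce by normal approximation. Masking would change neither sample size nor power. The issue is bias.

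**2. Exposed items.** Counting lines in Table 1, and treating contraception as medication data because Sections 6.2 and 6.3 collect it under medication use:
- Osteoarthritis: 3 of 4 lines (functional status, pain, assistive devices).
- RA: 1 of 8 (disease activity measure).
- Lupus: 0 of 6.

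**3. Illustrative size.** The documents give no rate of differential crediting. Assumptions: every line applies, each is met 70% of the time, items are independent, and each note-based item is credited 5 to 10 percentage points more often in the intervention arm, averaged over all patients. SD of the count = √(J × 0.7 × 0.3) for J lines; shift = note-based lines × 0.05 to 0.10; share of target = (shift/SD)/0.5.

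| Column | J | Note-based | SD | Shift (items) | Shift (SD) | Share of 0.5 SD |
|---|---|---|---|---|---|---|
| Osteoarthritis | 4 | 3 | 0.917 | 0.15-0.30 | 0.164-0.327 | 33-65% |
| RA | 8 | 1 | 1.296 | 0.05-0.10 | 0.039-0.077 | 8-15% |
| Lupus | 6 | 0 | 1.122 | 0 | 0 | 0% |

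**4. Sensitivity of the illustration.**
- Contraception counted as note-based: RA has 2 lines, 0.10-0.20/1.296, or 15-31%; lupus has 1 line, 0.05-0.10/1.122, or 9-18%.
- Inter-item correlation of 0.2 (assumed): the SD is multiplied by √(1 + 0.2(J − 1)). Osteoarthritis: 0.917 × 1.265 = 1.159, giving 26-52%. RA: 1.296 × 1.549 = 2.008, giving 5-10%.
- Phrase present in half of intervention notes (assumed), with no other clue to arm: the shift halves, so osteoarthritis becomes 16-33%.
- Fewer applicable lines push the other way. Without the three RA lines tied to methotrexate or a teratogenic drug, J = 5, SD = √(5 × 0.21) = 1.025, and RA becomes 10-20%.

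**5. Effect on the test.** The disease mix is not given, so the trial-wide bias cannot be fixed. With SE 0.169 and no true effect, a trial-wide shift of 0.05, 0.10, 0.20 or 0.30 SD raises the chance of a significant result from 5% to about 6%, 9%, 22% or 43% (normal approximation). The primary score also covers chart-review patients. With an assumed 30 per provider and ICC 0.02, n = 300/1.58 = 189.9 and SE = 0.103; a shift of 0.10 to 0.20 SD then gives 16% to 50%. More charts shrink the SE but not a systematic bias.

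**The case against.** Three stronger readings are tempting, and the documents support none of them.

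- A reader might infer that the intervention arm is coached to chart the quality items. The coaching covers only the individuation question and its smart phrase, and no Table 1 item is one of those questions. Answers about a typical weekday or a health priority might be read as a functional or pain assessment, but that spillover is inference. Moreover, recording a disease activity measure is itself a listed metric, so more of it in one arm is not automatically bias.
- A reader might infer that the plan has one person both check uptake and score the outcome. It does not say who does either task, or in what order. What stands is that nothing separates them. Section 10 refers to a Manual of Operating Procedures that is not among the documents reviewed; abstraction rules may be in it.
- A reader might take the whole score as compromised. Most lupus and RA lines are prescriptions, laboratory tests, imaging, screening or vaccinations, for which RPDR and EDW are named as sources. Notes without the phrase do not reveal the arm by that route.

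The masking of the PI and Co-Is is real and covers the data they see for analysis. It does not reach whoever reads identifiable notes. It is also fair to say that removing the phrase cannot fully mask an abstractor who sees the provider's name, with only 20 providers in the trial. That limits the remedy but does not close the gap.

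**Conclusion.** The concern holds as a gap in protection: the protocol and SAP do not shield scoring of the note-based primary items from knowledge of arm. It falls mainly on osteoarthritis, slightly on RA and hardly at all on lupus. The percentages in the working are illustrations that rest on the assumed 5-10 point difference in crediting, not estimates of bias in this trial. Neither the presence of bias nor its trial-wide size can be established from the documents, and the power calculation is unaffected. The change is worth making before abstraction starts, because a score abstracted with the arm in view could be repaired only by abstracting again.

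**What to change.** Add to Sections 6.5 and 9:

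1. Fill prescription, laboratory, imaging and vaccination items from RPDR/EDW by program, and state the source of every Table 1 item.
2. Have note-based items scored by existing staff who did not meet or coach intervention providers, without the arm list, and with provider name and smart-phrase text removed where feasible. Lock the score before any uptake check.
3. Run the uptake check afterwards as an electronic text search, applied identically in both arms.
4. Pre-specify a sensitivity analysis of the primary GEE model using only items verifiable from orders or results, reported beside the full score.

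The cost is resequencing existing chart work, a text filter, one extra model run and a few lines of protocol. There are two downsides. Masking will be imperfect with 20 known providers. The restricted score drops most osteoarthritis items and may miss care recorded only in free text, so it should remain a sensitivity analysis and not replace the primary score. Steps 1 to 3 reduce detection bias; only step 4 speaks to possible documentation spillover.

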## 3. Chart reviews

We will examine the charts of patients with lupus, osteoarthritis, or inflammatory arthritis seen >1 time by enrolled providers in both the intervention and control arms during the 6 months following provider enrollment, beginning  $\geq 1$  month after the date the provider takes the IATs. As indicated above, we will not obtain informed consent for patients of consented providers who will not be audiotaped but whose charts will be reviewed. Patients who were reached and invited to participate in the audiotaped encounter and surveys and did not consent or opted out of participation when approached will not have their chart reviewed. Patients who were not approached, or who were sent letters but could not be reached by phone or in person and did not opt out and are seen during this time frame by providers who are part of this study, may have their charts reviewed. We plan to collect demographics, social determinants of health, comorbidities/diagnoses, quality metrics related to their rheumatic disease, lab results, preventive care use (including immunizations), healthcare utilization (including ED visits, hospitalizations, outpatient visits and appointment no shows), medication use (including use of contraception as a quality metric), and medication refill data over the 6 months following the date of the recorded encounter. We will also see if any of the individuation

statements (smart phrases) were used for patients not specifically enrolled in the intervention (spillover from practice changes by the provider).

